### 6.5.1. Participants data

#### Baseline

- Investigating center code (automatic)
- Participant ID number (automatic)
- Participant date of birth (month/year)
- Gender
- Date of information on the study
- Date of inclusion in the study
- Dependency index : AG-GIR (Autonomie Gérontologie Groupes Iso Ressources) score
- Vaccination status (Covid19, Influenza, Pneumococcal)
- Comorbidities

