### 7.1. Number of centers and individuals to include

Each Nursing Home will have an approximate size of 90 participants, with a small coefficient of variation. It is estimated that 80% of participants will be present in both periods. As recruitment is open to new participants, those who die or permanently leave their Nursing Home will be replaced, and the number of participants present in each Nursing Home will remain constant throughout the study.

The intra-cluster coefficient of variation (WP-ICC  $\rho$ ) is estimated at 0.1 (10% of ARIs are explained by the Nursing Home environment). The inter-period correlation (between-period ICC  $\eta$ ) is estimated to be negligible (the two periods are winter and one year apart). Cluster auto-correlation (CAC) is set at 0.5 (i.e.  $\eta=0.05$ ), a figure recommended when few hypotheses are involved (Giraudeau *et al*, Sample size calculation for cluster randomized cross-over trials. Stat Med 2008;27:5578-85). Individual auto-correlation (IAC) is set at 0.2. Assuming an ARI incidence of 17 per 100 patient-years in the absence of UVCI devices, it is estimated that 12 clusters need to be included to demonstrate a 50% reduction in ARI incidence, with a two-sided alpha risk of 0.05 and power of 80% (Kasza *et al*, Sample Size Calculation for Stepped Wedge and Other Longitudinal Cluster Randomised Trials. Stat Med 2020;39:1871-83; Hooper *et al*, Sample size and power calculations for open cohort longitudinal cluster randomized trials. Stat Med 2016;35:4718-28)

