### Main analysis

The main comparison will focus on the incidence of first severe ARI between follow-up periods with an unfiltered UV device and follow-up periods with a filtered UV device. The numerator will be the number of people who experienced at least one severe ARI during a period. The denominator will be the cumulative time spent in the nursing home until the first ARI or exit from the period.

The result will be expressed as an incidence ratio with a 95% confidence interval.

In the first instance, the analysis will be carried out at the individual level. A generalized linear mixed model will be used, with a Poisson distribution or a negative binomial distribution in the case of overdispersion, a logarithmic link function and an *offset* term for the number of patient-years. The model will take into account not only intervention and period fixed effects, but also random effects at cluster, cluster-period, cluster-individual and individual levels. The correlation structure will be of the exchangeable block type.

In the second instance, if the model does not converge, we will perform the analysis at the cluster level (Hayes RJ, Moulton LH. *Cluster Randomised Trials*. CRC Press; 2017. <https://books.google.fr/books?id=iklrDwAAQBAJ> p197).

Sensitivity analyses will be carried out:

- Using the cumulative incidence of severe ARI as the endpoint, with the total number of severe ARI in the numerator and the cumulative time spent in the nursing home until exit from the period in the denominator. The model will be the same as the main model, with the addition of a random individual-period effect.
- By adjusting the model on the following variables: gender, age, GIR index. The last two variables will be measured at the start of each period.

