### Analysis of clinical secondary endpoints

- Analyses of clinical secondary endpoints will focus on:
  - Incidence of symptomatic ARIs of all grades
  - Incidence of all-cause hospitalization, all-cause mortality, and all-cause "hospitalization or death"
  - Incidence of non-infectious adverse events of interest, overall and by severity grade (CTCAE classification).
- Analyses of clinical secondary endpoints will focus on the occurrence of the 1st event and will be performed without adjustment. Sensitivity analyses will be performed:
  - Using cumulative incidence as the endpoint
  - By adjusting the model on the following variables: age, gender, GIR index.
- Analyses of clinical secondary endpoints will use the same model as that used for the primary analysis, or equivalent models appropriate to the frequency of events.

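### The primary and clinical secondary analyses are valid but rank the adjusted model second; promoting it, with GIR taken at first inclusion, is a small and nearly free gain

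*Protocol*

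**What the plan says.** Protocol section 7.2, Main analysis, defines the primary model: "The model will take into account not only intervention and period fixed effects, but also random effects at cluster, cluster-period, cluster-individual and individual levels". It contains no resident characteristics. The adjusted model appears under the sensitivity analyses, "By adjusting the model on the following variables: gender, age, GIR index", and for age and GIR the protocol adds: "The last two variables will be measured at the start of each period". The Summary gives the same ranking.

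Under Analysis of clinical secondary endpoints, the first-event analyses "will be performed without adjustment", again with an age, gender and GIR model as sensitivity analysis.

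Section 6.5.1 lists date of birth (month and year), gender and "Dependency index : AG-GIR (Autonomie Gérontologie Groupes Iso Ressources) score" among the baseline items. The Missing data paragraph of section 7.2 allows multiple imputation for explanatory variables missing in under 10% of participants, and drops from multivariate analyses those missing in more than 10%.

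**The concern.** The crossover removes stable differences between homes. It does not remove changes in a home's resident mix from one winter to the next. Section 7.1 expects 80% of participants to be present in both periods, and those who leave are replaced. The period effect absorbs drift common to all homes but not drift specific to one home, and 12 homes balance such drift only roughly.

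The adjusted model is already specified and its data are already collected, so placing it second gives up whatever precision and balance it offers. The order also decides which result is the headline if the two models disagree, so it should be settled before unblinding.

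**Working it through.** **Inputs (section 7.1).** K = 12 homes; m = 90 residents per home ("Each Nursing Home will have an approximate size of 90 participants, with a small coefficient of variation"); within-period ICC ρ = 0.1; cluster autocorrelation CAC = 0.5; individual autocorrelation IAC = 0.2; share present in both periods r = 0.8; control rate 17 per 100 patient-years; 50% reduction; two-sided alpha 0.05. Each period runs 212 days (October 1 to April 30). The protocol gives no prognostic strength for the covariates, so every share explained below is an assumption.

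**Variance of the treatment effect.** Var = (2σ²/K) × [ρ(1 − CAC) + (1 − ρ)(1 − r × IAC)/m]
- Cluster-period part: 0.1 × 0.5 = 0.0500
- Individual part: 0.9 × (1 − 0.8 × 0.2)/90 = 0.756/90 = 0.0084
- Sum: 0.0584, equivalent to a design effect of 90 × 0.0584 = 5.256
- Individual share: 0.0084/0.0584 = 14.4%; cluster-period share: 85.6%

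**The protocol's own figure.** Section 7.1 says "it is estimated that 12 clusters need to be included to demonstrate a 50% reduction in ARI incidence", at 80% power. With binomial variance and a normal test, power at 12 homes is 0.740 if 0.17 is read as the risk per period (about 14 homes needed). It is 0.484 if the rate is converted to 7 months, 0.17 × 212/365 = 0.099 (about 26 needed). The stated 80% is not reproduced under a two-sided test. That is a separate matter; these two powers serve here only as starting points.

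**Gain if covariates explain a share R² of the individual part.** Ratio of variances = [0.05 + 0.0084 × (1 − R²)]/0.0584

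| R² (assumed) | Variance ratio | SE lower by | Power, 7-month risk | Power, 0.17 as risk |
|---|---|---|---|---|
| 0 | 1 | – | 0.484 | 0.740 |
| 10% | 0.05756/0.0584 = 0.986 | 0.7% | 0.489 | 0.746 |
| 20% | 0.05672/0.0584 = 0.971 | 1.4% | 0.495 | 0.753 |

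These shares are generous. If the rate ratio per SD of the prognostic score is 1.3 to 2.0 (assumed), R² = p²[exp((ln RR)²) − 1]/[p(1 − p)]. That gives 0.8-6.8% at p = 0.099, where the SE falls by at most 0.5%, and at most 12.6% at p = 0.17, where it falls by 0.9%. With an ICC of only 0.01 the individual share would be 64.9%, yet R² = 10% would still lower the SE by only 3.3%.

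**Chance case-mix change from turnover.** Suppose 20% of residents are replaced at random and the covariates of those who stay do not change. The treatment contrast of a standardised covariate then has SD √[2 × 0.2/(12 × 90)] = 0.0192. Multiplied by ln RR, this moves the log incidence ratio by SD 0.005 (RR 1.3) to 0.013 (RR 2.0). The SE of the log ratio at the 7-month risk is 0.37-0.39, so the shift is under 4% of one SE, or roughly 0.1% of the variance.

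**If the covariates also explained the cluster-period part.** The same 10% or 20% of both parts would lower the SE by 1 − √0.9 = 5% or 1 − √0.8 = 11%. This requires case mix to change by whole homes.

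**Model burden.** Patient-years per condition: 12 × 90 × 212/365 = 627. Expected events: 0.17 × 627 = 107 control and 0.085 × 627 = 53 active, about 160 in all.

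**The case against.** The strongest reply is that nothing here is wrong. An unadjusted primary analysis of a randomised trial is valid, the adjusted model is already pre-specified for both sets of endpoints, and on the figures above the swap buys almost nothing. That stands, and it is why the point is minor.

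Two technical objections also stand, against promoting the adjusted model exactly as written. GIR measured at the start of period 2 comes after a resident's possible exposure in period 1, so it could be affected by the assigned sequence. And under the Missing data paragraph, a covariate missing in more than 10% would drop out, so the primary model would depend on observed missingness. Taking GIR at first inclusion answers the first objection, and a missing-data rule fixed in advance answers the second.

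A further objection is that a model with four random-effect levels and a planned fallback for non-convergence should not be enlarged. With about 160 expected events, covariate terms for age, gender and GIR are a small burden, though not zero.

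A reader might infer that resident turnover is a major source of the dominant cluster-period variance, so that adjustment would cut the total variance by 10-20%. The protocol does not support this. Random 20% turnover contributes roughly 0.1%. Larger shifts would need home-level change, for which no figure is given; section 5.2 excludes homes planning major structural change, and section 6.5.2 records unforeseen ones.

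**Conclusion.** The point holds as a minor improvement. The protocol places an already specified adjusted model second, although its covariates are collected. At the protocol's own ICC, CAC, cluster size and retention, promoting it lowers the SE by about 0.7-1.4% if the covariates explain 10-20% of individual-level variance. That share is assumed, and the gain is smaller at the weaker prognostic strengths tried above. The turnover figure holds the covariates of staying residents fixed; GIR can change, so it is a lower bound, but the effect remains small.

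Two stronger conclusions should not be drawn. The unadjusted analyses are not invalid: each home is its own control, residents, staff and investigators are not told about the filters, and chance home-by-winter variation is carried by the cluster-period random effect. Nor does adjustment repair the gap between the recomputed and the stated power: half a point to just over one point does not close it.

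**What to change.** Before unblinding, in section 7.2, the Summary and the analysis plan:

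- Make the model adjusted for age, gender and GIR the primary analysis for the primary and clinical secondary endpoints. Use GIR as recorded at the resident's first inclusion, not re-measured at the start of period 2. Age may still be taken at the start of each period, since the intervention cannot change it.
- Fix one simple rule for missing GIR, for example a single imputed value or a separate missing category, applied without knowledge of allocation. State that the 10% rule does not apply to the primary model.
- Say how the covariates enter the cluster-level fallback, or that the fallback is unadjusted.
- Keep the unadjusted model as the sensitivity analysis.

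The cost is swapping two models already planned, slightly more model complexity, a few imputed GIR values and, for residents present in both winters, a GIR about a year old in period 2. Section 13.2 sends every protocol amendment to the ethics committee, so there is an administrative step. No new data are needed.

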### Analysis of clinical secondary endpoints

- Analyses of clinical secondary endpoints will focus on:
  - Incidence of symptomatic ARIs of all grades
  - Incidence of all-cause hospitalization, all-cause mortality, and all-cause "hospitalization or death"
  - Incidence of non-infectious adverse events of interest, overall and by severity grade (CTCAE classification).
- Analyses of clinical secondary endpoints will focus on the occurrence of the 1st event and will be performed without adjustment. Sensitivity analyses will be performed:
  - Using cumulative incidence as the endpoint
  - By adjusting the model on the following variables: age, gender, GIR index.
- Analyses of clinical secondary endpoints will use the same model as that used for the primary analysis, or equivalent models appropriate to the frequency of events.

### Analysis of microbiological secondary endpoints

These secondary analyses will compare microbiological loads in air and fomite samples between periods when UVGI devices are unfiltered (active) versus filtered (inactive). The outcome will be expressed as cycle threshold (Ct) values and number of genome copies/m^3 for viral agents; and colony-forming units (CFU)/cm^2 for bacterial and fungal agents. Mean microbial loads will be compared using mixed-effects linear regression models, including random effects for cluster and period.

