#### Inclusion of individuals

All residents who have at least one day's presence in one of the participating centers during one of the two calendar periods of the study (period 1: between October 1, 2024 and April 30, 2025; period 2: between October 1, 2025 and April 30, 2026) will be eligible.

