#### Microbiological monitoring of air and surfaces

Environmental monitoring will be performed to quantify pathogen contamination in the air and on surfaces within nursing home communal areas. Air and surface samples will be collected at baseline and every seven weeks during both study periods.

Air samples will be obtained using volumetric air samplers operating at standardized flow rates. Surface samples will be collected using tryptic soy agar (TSA) contact plates and sterile polyester-headed swabs (eSWAB) applied to predefined fomites. Two self-adhesive plastic fomites will be installed in each center — one in a dining room and one in a communal activity room.

Air samples will be analyzed by quantitative PCR (qPCR) assays targeting SARS-CoV-2, influenza A and B viruses, and respiratory syncytial virus, using the *Triplex Thermo Fisher TaqPath COVID-19, FluA/B, RSV Combo Kit* (Ref. A49867). Surface samples will be processed for bacterial and fungal detection by culture on TSA plates, followed by species identification using matrix-assisted laser desorption/ionization time-of-flight mass spectrometry (MALDI-TOF MS, Bruker Daltonics). Viral detection from fomites will be performed by qPCR (see details in section 18.2).

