### 7.2. Data analysis

Details of the analysis methods will be set out in a specific document entitled "analysis plan", validated by the study's scientific board and made public before the start of the analysis.

The principles guiding the drafting of this analysis plan will be as follows:

General

- The analysis will be performed on an intention-to-treat basis, and will include all centers and all permanent residents, whatever their length of follow-up and reason for premature discharge from the center, with the exception of those who opted out.
- A two-tailed *p-value* of <0.05 is considered statistically significant.

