### Description of venue and protocol

Within each study ENHs, 2 sampling zones will be defined in :

- an activity room
- the main dining hall

These zones will remain the same throughout the study.

In each of these zones, the following will be carried out:

- For surface sampling: on one sampling surface: 2 surfaces for bacterial sampling, one surface for viral sampling. This sampling surface will be placed on a wall, with the bottom of the sampling surfaces at 170cm from the ground.
- For air sampling: samples will be taken at a distance of 200cm from the wall bearing the decontamination device, centered on the latter and at a height of 170cm.

Materials & methods :

*Surface sampling surface:* self-adhesive plastic plate. Each surface in each Nursing Home will be specifically identified by a unique code to facilitate sampling

*Cleaning of sampling surfaces:* After installation and after each sampling operation, surfaces must be thoroughly cleaned ( disinfectant wipe (30s), then cleaning wipe (30s), then isopropyl alcohol wipe (30s) ).

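### The microbiology model names random effects for cluster and period but no home-by-period effect, so its standard errors may be too small

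*Protocol*

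**What the plan says.** The microbiology paragraph of protocol section 7.2 compares loads between active and filtered periods and gives the model in one sentence: "Mean microbial loads will be compared using mixed-effects linear regression models, including random effects for cluster and period". It lists no fixed effects.

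The Main analysis paragraph of the same section sets out a fuller structure for the primary endpoint: "intervention and period fixed effects, but also random effects at cluster, cluster-period, cluster-individual and individual levels". The next paragraph extends it: "Analyses of clinical secondary endpoints will use the same model as that used for the primary analysis", or suitable equivalents. No such sentence covers microbiology.

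Section 7.2 leaves details to a separate analysis plan, which is not among the documents reviewed, but introduces its own statements with "The principles guiding the drafting of this analysis plan will be as follows".

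Other relevant places:
- Section 5.1 defines the periods by calendar date, for example "period 1: between October 1, 2024 and April 30, 2025".
- Section 6.2.2 on sampling: "Air and surface samples will be collected at baseline and every seven weeks during both study periods".
- Appendix 18.2: in each home "2 sampling zones will be defined in" an activity room and the main dining hall.
- Section 7.1, for ARI: "Cluster auto-correlation (CAC) is set at 0.5", with a within-period ICC of 0.1.

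**The concern.** All samples from one home in one winter share the same UVGI status. They also share whatever else happened in that home that winter, such as a local outbreak. A home effect removes what is constant in a home over both winters, and a calendar-period effect removes what is common to all homes in one winter. Neither removes a change peculiar to one home between winters. Without a home-by-period term, repeated samples from one home-winter count as independent evidence on UVGI.

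These endpoints would naturally be read as support for a mechanism behind the clinical result. Overstated precision could lend that mechanism support it has not earned.

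**Working it through.** The protocol states no power or error rate for the microbiological endpoints, so there is no figure of its own to reproduce. The check is the type I error of the stated model, with period read as calendar winter.

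**Inputs from the protocol.** 12 homes, randomised 1:1 (taken as 6 per arm), each crossing over once; two-sided 5% level. October 1 to April 30 is 212 days, or 30.3 weeks, so sampling rounds fall at weeks 0, 7, 14, 21 and 28. With 2 rooms, the number of room-visits per home-winter is m = 4 × 2 = 8 without week 0, or 5 × 2 = 10 with it.

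**Assumptions.** ICC 0.1 and CAC 0.5 are given for ARI and borrowed here. The outcome is taken as normal, with one value per room-visit and independent residuals.

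**Formulas.** Set the total variance to 1. Home-by-period variance h = ICC × (1 − CAC); residual variance e = 1 − ICC. The treatment estimate is half the difference between arms in the mean winter-to-winter change per home.
- True variance: (e + m·h) / (6m).
- Variance the stated model reports, on average: s² / (6m), where s² = e + 10·m·h / (24m − 14). The 24m − 14 residual degrees of freedom include only 10 from home-by-period differences.
- Ratio R = (e + m·h) / s².
- Type I error = 2·P(T > t_crit / √R) on 24m − 14 df.

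**At ICC 0.1, CAC 0.5 (h = 0.05, e = 0.90).**
- m = 8: true 0.90 + 0.40 = 1.30; s² = 0.90 + 4/178 = 0.922; R = 1.41. 1.973/√1.41 = 1.66, giving 9.8%.
- m = 10: true 0.90 + 0.50 = 1.40; s² = 0.90 + 5/226 = 0.922; R = 1.52. 1.971/√1.52 = 1.60, giving 11.1%.

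The true standard error is therefore √1.41 = 1.19 or √1.52 = 1.23 times the reported one.

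**Range.**

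| ICC | CAC | m = 8 | m = 10 |
|---|---|---|---|
| 0.02 | 0.5 | 5.9% | 6.1% |
| 0.05 | 0.5 | 7.3% | 7.9% |
| 0.1 | 0.5 | 9.8% | 11.1% |
| 0.2 | 0.5 | 15% | 18% |
| 0.1 | 0.8 | 6.9% | 7.5% |
| 0.1 | 1 | 5.0% | 5.0% |

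**Checks.** Simulation with 40,000 runs per case at ICC 0.1 gave 9.7% and 11.1% (CAC 0.5), 7.1% and 7.7% (CAC 0.8), and 5.2% and 5.1% (CAC 1). A t test on home-level differences (10 df) gave 4.9% to 5.2% throughout. In 250 REML fits at m = 10 and CAC 0.5, crossed random home and period effects gave 10.8%, against 5.2% with a home-by-period effect and fixed period (Monte Carlo SE of the first: √(0.108 × 0.892/250) = 2 points).

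**The case against.** **The words may mean period within home.** The opening sentence of the microbiology paragraph compares active with filtered periods, and in any one winter these differ by home. The Main analysis already takes period as fixed, and a random calendar effect would have only two levels. On this reading the needed term is present and nothing is inflated. The reading is possible and stands as a condition on the finding. Against it, the Main analysis names period and cluster-period as separate terms, and section 5.1 ties the periods to calendar dates.

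**Such detail belongs in the analysis plan.** The sentence says the model includes these effects, which need not be a full list. This is fair for fixed effects and degrees of freedom. It is weaker for the random effects, because the protocol does state them, and states them as principles that the plan will follow.

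**The size has no microbiological basis.** This stands: ICC and CAC are ARI design values, hence the range. Section 7.1 also calls the correlation between periods negligible before setting CAC at 0.5. A lower CAC would raise h and so enlarge the inflation.

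**Stronger readings that the documents do not support.**
- A reader might infer that a bad winter common to all homes biases the test, or that the two-level random period is itself the fault. UVGI status is balanced across winters, and a 1-SD shift common to all homes left the simulated rates at 9.8% and 11.1% (CAC 0.5) and 4.9% to 5.0% (CAC 1).
- A reader might infer that virus on fomites has no usable scale. Copies per m³ is an air unit, but the same sentence lists Ct values, which fit a swab.
- A reader might infer that an endpoint is lost because the objectives and the summary speak of presence while section 4.4 and the analysis speak of load. This is a wording mismatch with no shown effect on any result.

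**Conclusion.** The point holds in conditional form. As written, the microbiology model omits the home-by-period effect that the protocol uses for its primary endpoint. Read with calendar periods, and if homes change differently between winters, it overstates precision: about 10% to 11% type I error at the borrowed values, and 6% to 18% over ICC 0.02 to 0.2 at CAC 0.5. If home-by-period variance is zero, or period within home was intended, the error is 5% and only the wording needs repair.

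It would be wrong to conclude that the trial's main result is at risk. The primary analysis has the cluster-period term, and the clinical secondary endpoints follow that model or an equivalent. The correction should be made before analysis. Confidence is medium, because the finding depends on how one phrase is read and on borrowed variance components.

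**What to change.** In the microbiology paragraph of section 7.2, state fixed effects for intervention and period, random effects for home and home-by-period, and a small-sample correction (about 10 df for the UVGI contrast). Alternatively, use the cluster-level analysis already named there as the fallback for the primary endpoint. If period within home was meant, say so.

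In the same edit, as wording only: tie copies per m³ to air samples and Ct to fomite swabs, and use either presence or load consistently in the summary and sections 4.2, 4.4 and 7.2.

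The cost is one reworded paragraph and no new samples. Intervals for these secondary endpoints widen by √R × 2.228/1.960: 1.35 (m = 8) to 1.40 (m = 10) times at the borrowed values, 1.23 to 1.25 times at CAC 0.8, and 1.14 times if home-by-period variance is zero.
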